8.2.7 Outcome surveillance for Survival, AML/MDS transformation, and cytogenetic abnormality

All subjects received at least one dose of AMG531 will be assessed for the following parameters. The results of the survey will be reported using the outcome surveillance form (refer to Attachment 1 of the Study Protocol Supplement).

- 1) Parameters
 - Survival (date of confirmation) or death (date and cause of death).
 - Presence or absence of cytogenetic abnormality (date of confirmation, cellularity of bone marrow, karyotype by cytogenetic report)
 - Presence or absence of fibrosis according to reticulin grade (reticulin stain/trichrome stain (Appendix 1))
 - Presence or absence of AML or MDS transformation (date of initial diagnosis in case of presence, or date of last confirmation in case of absence)
 - Presence or absence of Hematopoietic Stem Cell Transplantation (date of transplantation, or the last date of confirmation in case of absence)
- 2) Timing of assessment
 - Approximately 3 years after the initial administration of AMG531 and whenever required by the regulatory authority or investigators.

9 ADVERSE EVENTS

9.1 Definition of adverse events

An adverse event (AE) is herein defined as any untoward medical occurrence in subjects received AMG531. An AE can therefore be any unfavorable or unintended sign (including an abnormal laboratory finding), symptom or disease, regardless of causal relationship to AMG531. An adverse drug reaction (ADR) is defined as any AE of which causal relationship to AMG531 cannot be ruled out (any events assessed to be other than “unlikely” or “not related”).

Laboratory results (hematology, serum chemistry, blood iron-related parameters, blood coagulation and fibrinolysis) will be evaluated for deviations (abnormalities) from normal range of each investigative site. In the event of an abnormal value (abnormal change), clinical significance of the abnormal change in comparison with baseline will be assessed. In consideration of pharmacological effects of AMG531, an increase in platelet, hemoglobin, reticulocyte, and/or neutrophil will be treated as abnormal only in the cases where the investigator considers it to be medically important.

For signs, symptoms, and abnormal laboratory findings associated with a disease (diagnosed disease), the disease will be treated as an AE. If any atypical sign is observed in that disease, the sign will be treated as an individual AE.

Observation period of both non-serious and serious adverse events will be the period between the start of study treatment through to the end of study visit or 4 weeks after the last administration of AMG531, whichever is longer. However, any event reported as delayed toxicity or the like attributed the investigational product will be treated as an adverse event as well.

9.1.1 Definition of serious adverse events

A serious adverse event (SAE) is any adverse event that:

- 1) Results in death;
- 2) Is life-threatening;
- 3) Requires inpatient hospitalization or prolongation of existing hospitalization (excluding a hospitalization needed for medical examinations and a hospitalization planned before the start of the study);
- 4) Results in disability/incapacity;
- 5) Results in potential disability;
- 6) Results in other conditions as important as 1) to 5); or
- 7) Is a congenital anomaly/birth defect.

9.1.2 Definition of other significant adverse events

Other significant AEs are defined as any events other than those reported as SAEs that lead a subject to treatment interruption, dose reduction or withdrawal.

9.2 Safety assessment parameters

For safety assessment, the following parameters will be investigated.

The investigator will follow subjects with AEs until the event has recovered to the pretreatment level or archived the condition which is not clinically important, excluding the cases where the investigator considers that the safety of the relevant subject is sufficiently assured and further follow-up is not necessary. Any action taken for the AE during the follow-up will be recorded on the eCRF.

- 1) Name of AE
- 2) Date of onset
- 3) Severity

Severity will be graded using the 5-point scale, Common Terminology Criteria for Adverse Events (CTCAE) version 4.0. AEs to which the CTCAE severity scale is not applicable will be graded as described below:

- Grade 1: Mild; asymptomatic or mild symptoms; clinical or diagnostic observations only; intervention not indicated.
- Grade 2: Moderate; minimal local or noninvasive intervention indicated; limiting age-appropriate instrumental active daily living (preparing meals, shopping for groceries or clothes, using the telephone, managing money, etc).
- Grade 3: Severe or medically significant but not immediately life-threatening; hospitalization or prolongation of hospitalization indicated; disabling; limiting self care active daily living (bathing, dressing and undressing, self feeding, using the toilet, taking medications, and not bedridden).
- Grade 4: Life-threatening consequences; urgent intervention indicated.
- Grade 5: Death related to AE

4) Seriousness

- Serious: Events defined in Section 9.1.1.
- Non-serious: Events other than those defined in Section 9.1.1.

5) Actions taken for the study treatment

- None/not applicable
- Dose reduced
- Dose interrupted
- Discontinued

6) Other actions taken

- None
- Other medication prescribed or concomitant medication changed, etc.

7) Outcome

- Resolved/recovered
- Resolving/recovering

- Not resolved/not recovered
 - Resolved/recovered with squeal
 - Death
 - Unknown
- 8) Date of outcome assessment
- 9) Causal relationship to investigational product

Causal relationship to investigational product will be determined using the following 5-point scale.

- Certain
- Probable
- Possible
- Unlikely
- Not related

9.3 Actions to be taken on occurrence of an adverse event and follow-up

9.3.1 Actions for Subjects

If an AE occurs, the investigator will take appropriate actions as needed, including providing proper medical care and discontinuing study treatment in order to ensure the subject's safety.

9.3.2 Notification to the concerned parties (reporting to relevant personnel)

9.3.2.1 Serious adverse event

- 1) If a SAE occurs, regardless of the causal relationship with AMG531, the investigator will immediately (within 24 hours of the investigator becoming aware of the event) notify the sponsor or the designee in person or by phone, e-mail, or fax (using the SAE Report or a form prescribed by the investigative site) and will promptly (within 7 days of the investigator becoming aware of the event) submit a detailed written report to the sponsor or the designee and the IRB. When reporting to the IRB, unexpected serious adverse reactions should be identified.
- 2) The investigator is obligated to pursue and provide additional information upon request from the sponsor or the designee, the directors of investigative sites and the IRB.
- 3) The director of the investigative site will discuss with the IRB whether to continue the study at their site, if applicable.

- 4) In the case of serious and unexpected ADRs that are fatal or life-threatening, the sponsor or the designee should expedite the report to all concerned investigators, to the IRBs where required, and to the regulatory authorities within 7 days after first knowledge by the sponsor. Serious, unexpected reactions (ADRs) that are not fatal or life-threatening must be filed within 15 days after first knowledge by the sponsor.

9.3.2.2 Non-serious adverse events

If a noteworthy but non-serious AE occurs, the investigator will promptly provide the sponsor with a description of the event and the action taken. Other adverse events will be recorded in the eCRF.

9.3.3 Follow-up of adverse events

The investigator will follow subjects with AEs until the event has recovered to the pretreatment level or archived the condition which is not clinically important, excluding the cases where the investigator considers that the safety of the relevant subject is sufficiently assured and further follow-up is not necessary. Any action taken for the AEs during the follow-up will be recorded in the eCRF.

10 MANAGEMENT OF SUBJECTS; MEASURE FOR PATIENTS' SAFETY PROTECTION

10.1 Notification to other departments/hospitals

The investigator will check with the subject if he/she is scheduled to receive medical care or medications at any other department/hospital. If this is the case, the investigator will notify the relevant physician that the subject will participate in the clinical study. The investigator will identify the name of any medication that the subject has received other than those prescribed by the investigator as well as how it has been used. If the subject received platelet and/or RBC transfusion at any other department/hospital, investigations should be made in the same manner.

If the subject is newly receives medical care or medication at any other department/hospital during the study, the investigator will take actions same as above.

10.2 Contraception

Women of childbearing potential will be instructed to use one or more reliable methods of contraception (including condoms) throughout the study.

If the subject becomes pregnant or wants to have children during the study, the subject will be immediately withdrawn from the study.

10.3 Others

The eligibility of the subject to participate in the study will be strictly assessed through the screening test.

In addition, the study will be conducted in compliance with the study protocol, and the occurrence and severity of AEs and ADRs will be monitored throughout the study period and the appropriate actions will be taken when needed for the protection of subjects.

11 STOPPING RULES AND PROCEDURES

11.1 Subject withdrawal

11.1.1 Criteria for subject withdrawal

Any of the following circumstances will result in the subject being withdrawn from the study:

- 1) The subject is found to be ineligible for participation in this study due to violations in the inclusion or exclusion criteria specified in the study protocol;
- 2) The subject decides to discontinue his/her participation in the study;
- 3) The subject becomes unable to undergo necessary observations or examinations;
- 4) The subject who does not achieve a platelet response after 8-week treatment with AMG531 20 µg/kg QW;
- 5) The investigator considers that the subject should be withdrawn from the study due to an adverse event (including progression of the primary disease);
- 6) The subject received any of the prohibited concomitant medications or treatments;
- 7) The subject becomes pregnant or wants to have children during the study;
- 8) The investigator assesses that the subject needs to be withdrawn from the study for any reason not specified above.
- 9) The subject who does not meet the entry criteria for long-term treatment period

11.1.2 Procedure for subject withdrawal

If a subject is withdrawn from the study because of safety issues including occurrence of an adverse event, the investigator will provide appropriate treatment for the subject. For each subject withdrawn from the study, the investigator will check up the safety and

conduct the end of treatment and end of study procedures described in section 8.2.5 and 8.2.6 at withdrawal and follow him/her up as necessary until further monitoring is considered to be not required. If subject is withdrawn from the study due to safety issues and cannot conduct the scheduled end of treatment and end of study procedures, the end of treatment and end of study procedures described in section 8.2.5 and 8.2.6 will be conducted as soon as the study termination is decided. It is recommended that subjects withdrawn consent also return to the physician's office for the end of treatment and end of study examination for follow up.

Date and the reasons of study withdrawal, any medications given for the treatment during the follow up period, etc. will be recorded in the eCRF.

11.2 Premature termination or suspension of the study at a specific investigative site

If the investigator prematurely terminates or suspends the study at his/her site due to concerns over the safety of investigational product or for any other reason, the investigator will promptly notify the sponsor and IRB in writing, with a written detailed explanation. Also, if the investigative site's IRB says that the study should not be continued, the investigator will promptly notify the sponsor in writing, with a written detailed explanation on the study termination or suspension. The investigative site has major or continuous violations of GCP, the protocol or the clinical study agreements, the study will be prematurely terminated at the site. In such event, appropriate actions will be taken in the same manner to the above.

11.3 Premature termination or suspension of the entire study

When the entire study needs to be prematurely terminated or suspended, the sponsor will promptly inform all investigators, IRB, and the regulatory agency with a detailed explanation of the reason. When the study is prematurely terminated or suspended, the investigator will promptly brief subjects and take necessary measures including providing appropriate medical care.

12 STATISTICAL ANALYSIS

12.1 Statistical methods

Generally, categorical variables will be summarized by the number of subjects and the percentage of subjects in each category to the total number of subjects, and continuous variables will be summarized by descriptive statistics (number of subjects, mean, standard deviation, median, minimum, and maximum). Coefficient of variation and geometric mean will be also presented to summarize pharmacokinetic parameters.

Data will be cut off, collected and analyzed when all subjects complete the observations at week 17.

12.1.1 Efficacy

Platelet count measured within 7 days after platelet transfusion will not be subjected to the efficacy assessment. Likewise, hemoglobin concentrations determined within 28 days after RBC transfusion will not be subjected to the efficacy assessment. Neutrophil counts determined within 7 days of G-CSF as a rescue medication will not be used for the efficacy assessment.

Platelet count, hemoglobin concentrations and neutrophil counts determined in occasions other than in the scheduled visit in this study, including ordinary medical examinations and follow-up, will not be used for efficacy assessment.

12.1.1.1 Primary endpoint

The primary endpoints will be evaluated based on the Per Protocol Set (PPS). The proportion of subjects achieving a platelet response at Week 9, and two-sided 95% confidence interval will be calculated. Platelet response is defined as 1) achieving absolute platelet increase of $\geq 20 \times 10^9/L$ above baseline or 2) increase to $\geq 10 \times 10^9/L$ and by at least 100% from baseline.

Robustness of the results will be evaluated by the analysis calculated in the same manner based on the full analysis set (FAS).

12.1.1.2 Secondary endpoint

The secondary endpoint will be evaluated based on the PPS. The proportion of subjects with a platelet response in any time during the initial dose evaluation period, Week 1 through Week 12, Week 1 through Week 16, Week 1 through Week 24, and Week 1 through Week 52 or the proportion of subjects achieving platelet transfusion independency during the initial dose evaluation period, Week 1 through Week 12, Week 1 through Week 16, Week 1 through Week 24, Week 1 through Week 52, Week 1 through Week 104, and Week 1 through Week 156 will be calculated in the same manner as the primary variables. Platelet transfusion independence is defined as achieving transfusion free period of at least 8 consecutive weeks.

The proportion of subjects with erythroid and/or neutrophil response during the initial dose evaluation period as well as in Week 1 through Week 12, Week 1 through Week 16, Week 1 through Week 24, Week 1 through Week 52, Week 1 through Week 104, and in

Week1 through Week 156 will be calculated in the same manner as the primary variables. An erythroid response is defined as achieving an increase in hemoglobin concentration of ≥ 1.5 g/dL above baseline without transfusion or reduction in the transfusion unit by at least 4 units for 8 consecutive weeks compared with the pretreatment transfusion requirement in the previous 8 weeks prior to the first administration of AMG531 (Day -55 to Day 1). A neutrophil response is defined in those with ANC of $< 0.5 \times 10^9/L$ as a 100% increase over the baseline, or an increase in ANC of $> 0.5 \times 10^9/L$ in subjects with a pretreatment ANC of $< 1.0 \times 10^9/L$.

Time to platelet response and duration of platelet response will be summarized.

The change in platelet counts, hemoglobin concentrations, and neutrophil counts from baseline will be summarized at each scheduled visit. For the transfusion, only the platelet transfusion given due to platelet count of $< 10 \times 10^9/L$ (prophylactic transfusion) or due to bleeding (therapeutic transfusion) and RBC transfusions of which hemoglobin concentration is ≤ 9.0 g/dL or due to symptomatic anemia will be included in the response assessment.

The changes in bone marrow cellularity and reticulin grade will be summarized by each subject based on the test reports. The changes in the GIMEMA bleeding scale will be summarized.

Tri-lineage response is defined in those achieving platelet response, erythroid response, and neutrophil response all together. The proportion of subjects with tri-lineage response will be calculated in the same manner as the primary variables. Time to tri-lineage response will be summarized.

The proportion of subjects who achieved normal level for 8 consecutive weeks, who started tapering, and who discontinued study drug will be calculated. Time to achieving normal level for 8 consecutive weeks (the initial day of the period), to starting tapering, to discontinuing study drug as a result of tapering will be summarized.

Longest duration of drug discontinuation in subjects while maintaining stable response will be summarized.

Robustness of the results will be evaluated by the analysis calculated in the same manner based on the FAS.

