APTT	Activated partial thromboplastin time
█	█
AST	Aspartate aminotransferase
ATG	Anti-thymocyte globulin
AUC _{0-t}	Area under the serum concentration-time curve from time 0 to the last detectable time
BUN	Blood urea nitrogen
CI	Confidence Interval
█	█
C _{max}	Maximum serum concentration
CMML	Chronic myelomonocytic leukemia
Cr	Creatinine
CTCAE	Common Terminology Criteria for Adverse Events
D-Bil	Direct bilirubin
ECG	Electrocardiogram
ECOG	Eastern Cooperative Oncology Group
eCRF	Electronic case report form
EDC	Electronic data capture
FAS	Full Analysis Set
γ-GTP	γ-glutamyl transpeptidase
GCP	Good Clinical Practice, international standards for conducting clinical studies.
G-CSF	Granulocyte-colony stimulating factor
GPI-cell	Glycosyl phosphatidyl inositol-cell
Hb	Hemoglobin
█	█
Ht	Hematocrit
ICF	Informed Consent Form
IFN-γ	Interferon-γ
IST	Immunosuppressive therapy
ITP	Idiopathic (Immune) Thrombocytopenic Purpura
IRB	Institutional review board
IWRS	Interactive Web Response System
LIN	Lineage
LDH	Lactate dehydrogenase
NYHA	New York Heart Association
MCH	Mean corpuscular hemoglobin
MCHC	Mean corpuscular hemoglobin concentration

ABBREVIATION	DEFINITION
MCV	Mean corpuscular volume
MDS	Myelodysplastic syndromes
MedDRA	Medical Dictionary for Regulatory Activities
██████	████████████████████
███	████████████████████
███	████████████████████
██████████	██
PNH	Paroxysmal nocturnal hemoglobinuria
PPS	Per Protocol Set
PS	Performance status
PT-INR	Prothrombin time - International Normalized Ratio
PTs	Preferred Terms
RBC	Red blood cell
Ret	Reticulocyte
SDP	Single Donor Platelet
SID	Subject identification
SOC	System Organ Class
T-Bil	Total bilirubin
T-Cho	Total cholesterol
TIBC	Total iron-binding capacity
TMP	Thrombopoietin mimetic peptide
TNF- α	Tumor necrosis factor- α
T _{max}	Time to reach maximum serum drug concentration
TP	Total protein
TPO	Thrombopoietin
TSAT	Transferrin saturation : $TSAT = Fe \times 100 / TIBC$
UA	Uric acid
UIBC	Unsaturated iron-binding capacity
WBC	White blood cell

DEFINITION OF TERMS

Platelet Response

Platelet response is defined as (1) Absolute increase of $\geq 20 \times 10^9/L$ above baseline or, (2) Increase to $\geq 10 \times 10^9/L$ and by at least 100% from baseline.

Erythroid Response

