5.2 Inclusion criteria

Subjects may be included in the study if they meet all of the following criteria:

- 1) Patients who have provided written informed consent of their free will to participate in this clinical study. Written informed consent must be obtained prior to performing any study-related procedure
- 2) The subject is able and willing to comply with study procedures and follow-up as described in the protocol and ICF
- 3) Males and female subjects ≥ 19 years of age at the time of obtaining informed consent
- 4) Eastern Cooperative Oncology Group (ECOG) performance status (PS) score of ≤ 2 at the time of screening
- 5) Diagnosis of AA, confirmed by bone marrow and cytogenetic studies
- 6) Patient who is refractory to immunosuppressive therapy (IST)
- 7) Prior treatment with at least one course of horse or rabbit anti-thymocyte globulin (ATG) with cyclosporine
- 8) Thrombocytopenia defined as platelet $\leq 30 \times 10^9/L$
- 9) Fulfilling all of the following criteria in the screening examination
 - T-Bilirubin ≤ 1.5 times the upper limit of the laboratory normal range
 - ALT and AST ≤ 3 times the upper limit of the laboratory normal range
 - Creatinine ≤ 2.0 mg/dL

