- 11) Viral serologies for HIV, hepatitis B and C
- 12) 12-lead ECG
- 13) Flow cytometry of the peripheral blood for GPI-cells

8.2.2 Treatment Period: Week 1 (day of initial administration of AMG531) to Week 8

The following observations and examinations during the period of Week 1 (day of initial treatment with AMG531) through to Week 8 will be conducted on the day of study treatment, as a general rule. In consideration of convenience for subjects and investigational sites, \pm 3 days will be allowed except for the subjects assigned to the AMG531 concentration test group. Subjects on dose interruption will also undergo the same observations and examinations. Serum for the determination of AMG531 concentration can be collected at Week 1, Week 4 and Week 8 as described in [Table 8.2.2-1 Schedule for PK sampling](#).

- 1) Vital signs (systolic blood pressure, diastolic blood pressure and pulse rate)
Timing of measurement: Every week before dosing AMG531 in Week 1 to Week 8
- 2) Hematology (WBC, RBC, Hb, Ht, MCV, MCH, MCHC, PLT, Ret and WBC with differential count)
Timing of measurement: Every week before dosing AMG531 in Week 1 to Week 8
- 3) Serum chemistry (TP, ALB, T-Bil, D-Bil, AST, ALT, ALP, LDH, γ -GTP, T-Cho, UA, BUN, Cr, Na, K, Ca, P and Cl)
Timing of measurement: Every week before dosing AMG531 in Week 1 to Week 8
- 4) Blood iron-related parameter (ferritin)
Timing of measurement: Before dosing AMG531 at Week 1 and Week 5
- 5) Blood coagulation (D-dimer)
Timing of measurement: Before dosing AMG531 at Week 1 and Week 5
- 6) Serum AMG531 concentration

Timing of measurement: Before dosing and 4, 12, 24, 48, 72, 96, and 168 hours after dosing AMG531 at Week 1 and Week 8, and before dosing AMG531 at Week 4. Detailed time point with sampling time window is described in Table 8.2.2-1.

7) Serum TPO concentration

Timing of measurement: Before dosing AMG531 at Week 1

8) Antibodies against AMG531 and TPO

Timing of measurement: Before dosing AMG531 at Week 1 (Additional antibody test can be performed on subjects who show clinical findings suggested of possible antibody formation)

9) Cytokine assay

Timing of measurement: Before dosing AMG531 at Week 1

10) GIMEMA bleeding scale (Appendix 3)

Timing of measurement: Before dosing AMG531 at Week 1

Table 8.2.2-1 Schedule for PK sampling

Study Week	Study date	Time of Collection	
Week 1	Day 1	Before dosing of AMG531	within 2 hours
		After dosing of AMG531	4 hours ± 30 minutes
	12 hours ± 90 minutes		

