	24 hours ± 3 hours		
	48 hours ± 3 hours		
	72 hours ± 3 hours		
	Day 2		96 hours ± 3 hours
Day 3		168 hours ± 3 hours	
Day 4			
Day 5			
Day 8 ¹⁾			
Week 4	Day 22	Before dosing of AMG531	within 2 hours
Week 8	Day 50	Before dosing of AMG531	within 2 hours
		After dosing of AMG531	4 hours ± 30 minutes
	12 hours ± 90 minutes		
	24 hours ± 3 hours		
	48 hours ± 3 hours		
	72 hours ± 3 hours		
	Day 51		96 hours ± 3 hours
Day 52		168 hours ± 3 hours	
Day 53			
Day 54			
Day 57 ²⁾			

1) The examination at 168 hours after dosing AMG531 at Week 1 will be conducted before dosing AMG531 at Week 2

2) The examination at 168 hours after dosing AMG531 at Week 8 will be conducted before dosing AMG531 at Week 9

8.2.3 Treatment Period: Week 9 to Week 52

The following observations and examinations during Week 9 through to Week 52 will be conducted on the day of study treatment, as a general rule. In consideration of

convenience for subjects and investigational sites, ± 3 days will be allowed. Subjects on dose interruption will also undergo the same observations and examinations.

- 1) Vital signs (systolic blood pressure, diastolic blood pressure, and pulse rate)
Timing of measurement: Every week before dosing AMG531 at Week 9 through to Week 52
- 2) Hematology (WBC, RBC, Hb, Ht, MCV, MCH, MCHC, PLT, Ret and WBC with differential count)
Timing of measurement: Every week before dosing AMG531 at Week 9 through to Week 52
- 3) Serum chemistry (TP, ALB, T-Bil, D-Bil, AST, ALT, ALP, LDH, γ -GTP, T-Cho, UA, BUN, Cr, Na, K, Ca, P and Cl)
Timing of measurement: Before dosing AMG531 at Week 9, 13, 17, 21, 25, 29, 33, 37, 41, 45 and 49
- 4) Blood iron-related parameter (ferritin)
Timing of measurement: Before dosing AMG531 at Week 9, 13, 17, 21, 25, 29, 33, 37, 41, 45 and 49
- 5) Blood coagulation (D-dimer)
Timing of measurement: Before dosing AMG531 at Week 9, 13, 17, 21, 25, 29, 33, 37, 41, 45 and 49
- 6) Bone marrow biopsy and aspiration with cytogenetics (M/E ratio, cellularity of bone marrow, reticulin grade (reticulin stain/trichrome stain (Appendix 1)), iron stain, narrative pathology report, cytogenetic report and exploratory test described in section 3.3.4).
Timing of measurement: Before dosing AMG531 at Week 25 \pm 2 weeks
- 7) Serum TPO concentration
Timing of measurement: Before dosing AMG531 at Week 9
- 8) Antibodies against AMG531 and TPO

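### Any-time platelet response rests on one unconfirmed count among up to 51 weekly looks, so the share of unchanged subjects counted as responders can only rise with window length

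*Combined protocol and SAP*

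**What the plan says.** Definition of Terms and section 12.1.1.1 define platelet response by two alternatives: a rise of at least 20 ×10⁹/L over baseline, or "Increase to $\geq 10 \times 10^9/L$ and by at least 100% from baseline". Both are thresholds on a count. Neither asks for a repeat count or a minimum duration.

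Section 12.1.1.2 applies this definition to "The proportion of subjects with a platelet response in any time during the initial dose evaluation period, Week 1 through Week 12", and then to windows ending at Weeks 16, 24 and 52, all starting at Week 1. It also summarizes time to and duration of platelet response, without saying when a response starts.

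Hematology is scheduled weekly: "Every week before dosing AMG531 in Week 1 to Week 8" (section 8.2.2), then again each week from Week 9 to Week 52 (section 8.2.3). Section 12.1.1 drops counts within 7 days after a platelet transfusion and all unscheduled counts.

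Baseline platelet count is the mean of the two lowest counts in the 8 weeks before enrollment (Definition of Terms). Entry requires platelets of at most 30 ×10⁹/L (section 5.2, item 8).

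A confirmed platelet response is mentioned only in section 5.4, as a condition for entering long-term treatment. It is not part of the endpoint.

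**The concern.** An any-time endpoint takes the best of repeated looks. A subject whose platelet level never changes gets a new chance each week to cross the threshold by ordinary fluctuation. The windows are nested, so in a fixed set of subjects the share counted this way cannot fall as the window lengthens.

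No arm is untreated, so the trial cannot show how large that share is. Non-responders move up one dose level at Week 9 and may move further afterwards (sections 6.1.2 and 6.1.2.1). A rise in the any-time proportion from Week 8 to Week 52 would therefore naturally be read as benefit of longer treatment or escalation, although part of it would appear with no effect at all. Extension-period efficacy is a stated objective (section 2). With eight subjects per arm, one noise responder moves the arm's proportion by 1/8 = 12.5 percentage points. Tri-lineage response includes platelet response and inherits the problem.

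**Working it through.** The plan gives no expected response rate, error rate or variability for these endpoints, so it has no figure to reproduce.

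**1. Looks per window.** The Week 1 count precedes the first dose, so post-dose looks run from Week 2.

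| Window ends | Counts used | Looks |
|---|---|---|
| Week 8 | Weeks 2–8 | 7 |
| Week 12 | Weeks 2–12 | 11 |
| Week 16 | Weeks 2–16 | 15 |
| Week 24 | Weeks 2–24 | 23 |
| Week 52 | Weeks 2–52 | 51 |

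**2. Why 51 is a ceiling.** Section 11.1.1, item 4 withdraws subjects without a response after 8 weeks at 20 µg/kg. Take the fastest escalation in Table 6.1.2-1: one level at Week 9, then one every 4 weeks. A never-responder assigned 10 µg/kg reaches the top level at Week 17 and completes 8 weeks there at Week 25, which gives 24 looks. One assigned 1 µg/kg reaches it at Week 29 and completes 8 weeks at Week 37, which gives 36 looks. Steps after Week 9 are discretionary, so some subjects will have more. Transfusion exclusions and missed visits remove further looks.

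**3. Threshold.** With baseline b (×10⁹/L), a count is a response if it is at least min(b + 20, max(10, 2b)). This gives 10 at b = 5, 20 at b = 10, 40 at b = 20 and 48 at b = 28.

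**4. Accumulation over looks.** With a chance p of a false response per look and independent looks, the chance over k looks is 1 − (1 − p)^k. At p = 1% this gives 6.8, 10.5, 14.0, 20.6 and 40.1% for the five windows. At 24 and 36 looks it gives 21% and 30%.

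**5. Simplest case.** Set baseline equal to the true level, with lognormal counts and an assumed log-scale SD of 0.25.
- At level 10 or 20 the count must double: ln 2 / 0.25 = 2.77, so p ≈ 0.28%. Over 23 looks this gives 6%, and over 51 looks 13%.
- At level 28, ln(48/28) / 0.25 = 2.16, so p ≈ 1.55%. Over 23 looks this gives 30%, and over 51 looks 55%.

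**6. With the protocol's baseline.** The mean of the two lowest counts lies below the usual level, so the threshold is easier to cross. The assumptions are:
- four pre-study counts;
- stable lognormal counts with weekly autocorrelation 0 to 0.5;
- true level 10–28;
- subjects kept only if baseline is at most 30;
- all looks present.

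Percentage of unchanged subjects counted as responders on a single count:

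| Log-scale SD | Through Week 24 | Through Week 52 (ceiling) |
|---|---|---|
| 0.15 | about 1–2% | about 1–6% |
| 0.20 | 11–25% | 19–44% |
| 0.25 | 31–59% | 46–82% |

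The upper ends belong to true level 28. At true level 5 and SD 0.25 the figures are about 5–6% and 10–13%. For scale, eight unchanged subjects at SD 0.20 would yield 0.11 × 8 = 0.9 to 0.25 × 8 = 2.0 noise responders by Week 24.

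**7. With two consecutive qualifying counts.** On the same assumptions at SD 0.25 and true level 10–28, the rates are about 5–19% by Week 24 and 8–33% by Week 52.

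**The case against.** The size rests on a quantity the documents do not give. At SD 0.15 the effect is small. Higher autocorrelation shrinks it too: with baseline set at the true level, SD 0.25 and autocorrelation 0.8–0.9, the Week 52 figure is 6–9% at level 20 and 23–33% at level 28. The largest figures need a level near the entry limit and all 51 looks, while one randomization stratum lies at or below 10 (section 3.4). All of this stands, and it is why a range is given.

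The plan also has outputs that would expose a one-week response: duration of response, platelet change by visit, and transfusion independence and normal level, each over 8 consecutive weeks. That stands as well, but none of them alters the any-time proportion.

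Section 12.5 defers detail to an SAP finalized before database lock, so a rule could still be added there. Two consecutive counts is one of several reasonable rules, and replacing the planned proportion outright would be debatable. Reporting both versions meets that point.

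A reader might infer that time to response is planned to start at the single unconfirmed count. That is a natural reading, but the documents state no start rule.

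**Conclusion.** The point holds. One scheduled count suffices, no confirmation rule applies to the endpoint, and the share of unchanged subjects counted as responders can only rise with window length. The amount ranges from negligible to large. For true levels of 10–28 and log-scale SD 0.15–0.25 it runs from about 1% to 59% through Week 24. The Week 24 figures are the safer guide for persistent non-responders, because Week 52 assumes looks that many of them will not have. The ranges rest on the assumed SD, autocorrelation and four pre-study counts.

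Three stronger readings are tempting and not supported:
- **A type I error breach.** Section 12.2 sets no significance level, and these are descriptive secondary endpoints. The result is upward bias in a reported proportion.
- **Doubt about the primary endpoint on the same ground.** Week 9 is one fixed look, so accumulation over looks does not reach it.
- **A clean endpoint once confirmation is required.** The two-lowest-counts baseline leaves a residual bias, as step 7 shows.

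**What to change.** In the SAP, for each any-time window:
- Keep the planned single-count proportion, and report beside it the proportion meeting the criterion at two consecutive evaluable scheduled counts, dated at the first.
- Use that confirmed date as the start for time to and duration of platelet response.
- Base any statement about added response with longer treatment on the confirmed version, and say that confirmation reduces the bias without removing it.

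Leave the Week 9 primary endpoint as it is.

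The cost is a few SAP sentences and one extra line per table. The weekly counts are already collected, and no visit or treatment rule changes. The downside is that the confirmed proportions will be somewhat lower, and a response first seen at the last visit of a window cannot be confirmed within it.
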